In multivariate analysis, we will assess the incremental prognostic value of lipid-rich plaques by fitting proportional hazards regression models that include the max 4mm LCBI value and other identified prognostic variables. To identify the variables to be included in the multivariate model, we will perform a step-up regression blinded to the NIRS and IVUS data to identify the prognostic factors other than NIRS or IVUS data associated with the NC-MACE outcome. When that model has been selected, max 4mm LCBI will be added to the model to assess its incremental prognostic value. This will be the definitive test of Hypothesis 1. Results from these analyses will be used to estimate the net reclassification improvement, a measure of the incremental prognostic value of a new prognostic variable. Weighted estimation will also be required to calculate the NRI. Other covariates to be considered as possible prognostic factors in the NRI analysis include but are not limited to age (10 year units), hypertension, diabetes (any), current smoking (at the time of NIRS evaluation), prior history of coronary disease, history of cardiovascular disease, BMI, index catheterization presentation status (ACS, unstable angina, stable angina, and positive EST), total cholesterol level, use of statin therapy at discharge (as well as prior to index catheterization), requirement for at least 1 lesion treatment at the time of index catheterization), ADP antagonist at discharge, plasma lipid levels at baseline and during follow-up if available and history of renal insufficiency.

In a secondary statistical analysis, we will investigate whether the location of a large LRP within a blinded or non-blinded NIRS recording modifies its association with subsequent NC-MACE events.

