To test Hypothesis 2 (the Vulnerable Plaque Hypothesis), we will treat the individual coronary artery segments as separate units of observation, with appropriate adjustment for clustering of segments within patients. A study participant will typically provide results for up to 9 segments. To test this hypothesis, we will fit a proportional hazards regression model with max 4mm LCBI in the coronary artery segment as the measure of exposure and NC-MACE during 24 months caused by a new culprit lesion in that segment as the outcome. All models will include a categorical variable representing the type of coronary artery segment. To identify other characteristics of the coronary artery that should be included in this analysis, we will perform an initial analysis blinded to the value of max 4mm LCBI to determine whether segment type, segment length, or other characteristics of individual segments are risk factors for NC-MACE. Identified segment characteristics will be included in the model used to test the primary hypothesis. All analyses of coronary artery segments will use generalized estimating equations with robust variances to account for clustering of segments within patients.

As in the vulnerable patient analysis, we will investigate the predictive value of the binary variables defined by varying cut-points of max 4mm LCBI. The analyses using various cut-points will be used to calculate an ROC curve characterizing the prognostic value of presence of a lipid-rich plaque in a coronary artery segment. Weighted estimation will be required to estimate the ROC curve because of the exclusion from follow-up of 3,000 of the 9,000 enrolled patients with no segments with max 4mm LCBI \geq 250 in the follow-up cohort and analyses will account for clustering of segments within patients.

Results from the multivariate analyses will be used to estimate the net reclassification improvement obtained by considering max 4mm LCBI of individual segments as a risk factor. Weighted estimation will again be required to calculate the NRI. The covariates considered in the vulnerable patient analysis will again be considered in the vulnerable plaque analysis.

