6.2 SAMPLE SIZE CONSIDERATIONS

A total of 9,000 patients will be enrolled with multi-vessel scans. It is expected based on the PROSPECT Study that at least 720 patients (8%) will experience a NC-MACE event. We expect to find approximately 3,000 patients with large LRP (max 4mm LCBI \geq 250). All 3,000 of these patients will be followed with phone calls for 2 years to identify those who have an event. We expect to observe at least 300 events in this group. From the 6,000 with no or small LRP, a random sample of 3,000 patients will also be followed to determine their event rate, and to examine with IVUS and angiograms those in whom events occur. Of the approximately 2,700 patients with large LRP who do not have an event, a 300 person sample will be selected for IVUS and angiographic analysis to investigate characteristics of the yellow spots that did not lead to events.

Vulnerable Patient Analysis

For hypothesis 1, we will test the hypothesis that there will be no association between the baseline value of max 4mm LCBI (over the entire area scanned) and the incidence of NC-MACE.

In PROSPECT registry results, the 24-month cumulative incidence of NC-MACE in patients was approximately 10%. Subsequent STEMI literature indicates that patients with large LRP will have a higher rate than that observed in PROSPECT.

For the power calculations below, we assumed 6,000 evaluable patients, an event rate between 4 and 8% in the overall LRP study, and a two-sided alpha of 0.05 with a standard deviation of 100 for max 4mm LCBI. Table 2

provides values for the power of the study to detect the following effect sizes: hazard ratio of 1.18, 1.20, and 1.22 per 100 unit increase in max 4mm LCBI (calculated in PASS 12). These results demonstrate that the study will have 80% power to detect a minimal effect size of 1.18 per 100 unit increase in the max 4mm LCBI with 6,000 patients and an overall cumulative incidence of 5% at 24 months. As described in section 5.3, interim analyses will be performed at 6 month intervals.

Table 2: Hypothesis 1: Power Calculation for Vulnerable Patient Hypothesis

2 Year cumulative incidence overall, patient level	Relative Risk per 100 unit increase in max 4mm LCBI		
	1.18	1.20	1.22
8%	0.95	0.98	0.99
7%	0.92	0.96	0.98
6%	0.88	0.93	0.97
5%	0.82	0.88	0.93
4%	0.73	0.81	0.87

Vulnerable Plaque Analysis

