For hypothesis 2, we will test the hypothesis that there will be no association between the baseline value of max 4mm LCBI of the proximal, mid, or distal segment of a coronary artery and the incidence of NC-MACE.

For the vulnerable plaque analysis, we assumed that a patient will have a minimum of 50 mm of scanned target artery within at least 2 native epicardial arteries, yielding a minimum of 4 segments. Assuming that 24,000 segments (from 6,000 patients) will be available for analysis, a two sided alpha of 0.05 and a standard deviation of 100 LCBI units for max 4mm LCBI, Table 3 provides values for the power of the study to detect the following effect sizes: hazard ratio of 1.18, 1.20, and 1.22 (calculated by PASS 12). The study will have 80% power to detect a minimum effect size of 1.18 per 100 unit increase in the max 4mm LCBI with the minimum expected number of segments (24,000) and an overall cumulative incidence of 1.25% within the segments at 24 months.

Table 3: Hypothesis 2: Power Calculation for Vulnerable Plaque Hypothesis

2 Year cumulative incidence overall, segment level	Relative Risk per 100 unit increase in max 4mm LCBI		
	1.18	1.20	1.24
1.75%	0.92	0.96	0.98
1.50%	0.88	0.93	0.97
1.25%	0.82	0.88	0.93
1.00%	0.73	0.81	0.87
0.75%	0.60	0.69	0.76

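### The Vulnerable Plaque test (H2) is valid for a marginal segment association, but no specified analysis isolates the within-patient part, so rejecting H2 does not by itself show that LCBI locates the at-risk segment within a patient

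*Combined protocol and SAP*

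**What the plan says.** Section 6.1 tests H2 at the level of the coronary segment: "we will fit a proportional hazards regression model with max 4mm LCBI in the coronary artery segment as the measure of exposure". The outcome is an NC-MACE from a new culprit lesion in that segment. Segment type is always in the model, and other segment characteristics enter if a preliminary analysis blinded to LCBI identifies them. Clustering is handled through the variance: "All analyses of coronary artery segments will use generalized estimating equations with robust variances to account for clustering of segments within patients".

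On patient-level covariates the plan says: "The covariates considered in the vulnerable patient analysis will again be considered in the vulnerable plaque analysis". For H1 those covariates come from a plan to "perform a step-up regression blinded to the NIRS and IVUS data to identify the prognostic factors other than NIRS or IVUS data". The listed candidates are clinical and laboratory variables and medication. A patient-level LCBI term is not among them.

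On numbers, section 6.1 says "A study participant will typically provide results for up to 9 segments", and section 6.2 takes the 50 mm minimum scan as "yielding a minimum of 4 segments". Table 3 assumes 24,000 segments from 6,000 patients and "a standard deviation of 100 LCBI units for max 4mm LCBI".

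H2 is worded as an association between a segment's LCBI and events in that segment (synopsis, sections 2.1.2 and 6.1). Section 3.1 goes on to describe raised segment LCBI as marking raised risk for the particular segment. The synopsis and section 8.2 name both regional (local) and systemic therapy as possible next studies.

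**The concern.** One coefficient on the raw segment value pools two sources of association. Between patients, someone with lipid-rich arteries has higher LCBI in many segments and more events somewhere; that is the Vulnerable Patient question, which H1 already tests. Within a patient, the segment with the most lipid may be the one that later becomes the culprit; that is what a reader will take the Vulnerable Plaque result to mean. Robust variances make the standard error right for clustered segments. They do not separate the two components of the coefficient.

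Clinical covariates remove only the part of the between-patient signal that they happen to capture, and segment type removes only average differences by location. The segment-level ROC and NRI analyses (section 6.1), the secondary plaque hypotheses (section 3.2) and the 10 mm and 30 mm analyses (section 3.4) specify no within-patient contrast either. The IVUS comparisons in section 3.3 and the 300-person non-event sample in section 6.2 compare patients.

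What is at stake is the conclusion drawn from H2. The two components bear differently on local and on systemic therapy, and the pooled result alone does not tell them apart.

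**Working it through.** **Inputs from section 6.2.** HR 1.18 per 100 units; SD 100; two-sided alpha 0.05; 24,000 segments at 1.25% incidence, which is 24,000 × 0.0125 = 300 events. Segments per patient k = 4 (section 6.2 minimum) or 9 (section 6.1).

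**The plan's own figure.** Power = Φ(√D × SD × ln HR − 1.96), with SD in units of 100. √300 × 1 × 0.1655 = 2.867 and Φ(0.907) = 0.818. Table 3 gives 0.82, so the formula reproduces the plan.

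**A second event count.** Section 6.2 expects at least 720 events in 9,000 patients, at least 300 of them in the large-LRP group. Of the other 420, half are in the followed sample: 300 + 420/2 = 510. Using 510 for H2 assumes that every event can be assigned to a scanned segment.

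**Assumed limiting case.** Risk depends only on the patient's maximum LCBI (HR 1.18 per 100 units). The culprit segment is random within the patient, so the true within-patient effect is zero. Segments are exchangeable and normal with SD 100 and within-patient correlation ρ. The documents do not give ρ; 0.1 to 0.7 is used. No clinical adjustment is included.

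- The regression of the patient maximum on one segment has slope w = ρ + (1 − ρ)/k, so the pooled log HR is 0.1655 × w and z = 0.1655 × w × √D.
- For an analysis that isolates the within-patient part, information = D × (1 − ρ)(k − 1)/k. If the true within-patient HR were 1.18, power = Φ(0.1655 × √information − 1.96).

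Example, k = 4, ρ = 0.5, D = 300: w = 0.5 + 0.5/4 = 0.625; log HR = 0.1034, HR 1.109; z = 0.1034 × 17.32 = 1.79; rejection about 43%. Within-patient information = 300 × 0.5 × 0.75 = 112.5; z = 0.1655 × 10.61 = 1.756; power 42%.

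| k | ρ | w | Pooled HR | H2 rejected, 300 / 510 events | Power for within-patient HR 1.18, 300 / 510 events |
|---|---|---|---|---|---|
| 4 | 0.1 | 0.325 | 1.055 | 15% / 23% | 65% / 87% |
| 4 | 0.3 | 0.475 | 1.082 | 28% / 43% | 55% / 77% |
| 4 | 0.5 | 0.625 | 1.109 | 43% / 65% | 42% / 63% |
| 4 | 0.7 | 0.775 | 1.137 | 60% / 83% | 27% / 43% |
| 9 | 0.1 | 0.200 | 1.034 | 9% / 12% | 73% / 92% |
| 9 | 0.3 | 0.378 | 1.065 | 19% / 29% | 62% / 84% |
| 9 | 0.5 | 0.556 | 1.096 | 36% / 55% | 48% / 70% |
| 9 | 0.7 | 0.733 | 1.129 | 56% / 78% | 32% / 49% |

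The fifth column is the limiting case. The last column is a different truth, a real within-patient effect, and shows what the added model could detect.

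**Simulation check.** 6,000 patients × 4 segments, about 300 events, 150 replicates per setting, same limiting case. The pooled Cox model with segment type and patient-clustered variance rejected H2 in 25%, 46% and 64% at ρ = 0.3, 0.5 and 0.7. A patient-stratified model gave within-patient HRs of 0.994 to 1.007 and rejected in 4–5%. With no LCBI effect at all, the pooled test rejected in 5–7%, so the robust variance does its job.

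**Effect of the SD assumption.** Section 6.2 uses SD 100 for both levels: "a two-sided alpha of 0.05 with a standard deviation of 100 for max 4mm LCBI" for patients and the same figure for segments. Under the scenario with segment SD 100, the patient maximum has SD 74–92 (k = 4) or 65–90 (k = 9). If the segment SD is raised to 109–154 so that the patient maximum has SD 100, rejection at 300 events becomes 24.4, 39.6, 54.5 and 67.5% (k = 4) or 14.3, 30.9, 48.9 and 64.9% (k = 9).

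**The case against.** The strongest reply is that nothing here is an error. H2 asks whether segments with higher LCBI are more likely to cause NC-MACE, and a pooled segment model answers that. In a prognostic study a high-LCBI segment does carry higher risk, whatever share of that risk is common to the patient. This stands, and it is why the primary test should not change.

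The plan also does not ignore location. The synopsis has a committee blinded to NIRS locate the new culprit lesion, and the core laboratory compares that location with the baseline NIRS findings. This bears on the point but does not settle it, because no model, estimate or decision rule is attached to the comparison. The analysis examples in section 3.2 and the covariate list in section 6.1 are open-ended, but neither promises a within-patient analysis.

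The limiting case is also extreme. Section 2.1 cites a cross-sectional study in which LCBI above 400 separated STEMI culprit sites from other parts of the same artery, and a natural-history study in which lesion-level event rates differed widely by lesion features. A purely patient-level effect is therefore not the expectation. Clinical adjustment was not simulated and could lower the figures. At ρ = 0.1 and 300 events the rejection rate is only 9–15%.

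A reader might infer that H2 has an inflated type I error, or that the early-stopping rule in section 6.3 is unsound. The documents do not support that: in the limiting case the marginal null is false, so its rejections are correct. Nor does rejecting H2 commit anyone to local therapy, since the treatment study needs its own protocol and ethics approval, and both routes are left open.

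**Conclusion.** The point holds as one about interpretation. The planned H2 test is valid for the marginal segment association. Its single coefficient mixes between-patient and within-patient association, and no specified analysis isolates the second. Rejecting H2 therefore does not by itself show that LCBI picks out the at-risk segment within a patient, although the plan poses patient and plaque as two separate primary questions.

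The possible size ranges from small to large. It depends on a correlation that the documents do not give, on the limiting scenario, on normal exchangeable segments, on the absence of clinical adjustment and on the event count. The table measures how far H2 can be rejected without any site-level effect; it does not predict this trial. The change is worth making because it is cheap and because, without it, the planned output cannot show which situation holds.

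**What to change.** Leave the primary H2 test, its significance level and the stopping rule as they are. Add one pre-specified supportive model to section 6.1:

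> Segment max 4mm LCBI will be split into the patient's mean over analysed segments and the segment's deviation from that mean, fitted with the same covariates as the final primary H2 model and patient-clustered robust variance. The deviation hazard ratio and 95% CI will be reported beside the pooled H2 result, which will be described as a marginal segment association. Any claim of within-patient site prediction will cite the deviation estimate. A non-significant deviation estimate will not be read as no site-level effect.

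A patient-stratified Cox model may be named as a sensitivity analysis, not as an alternative, so that no choice is left until after unblinding. It has the merit of not depending on how many segments form the patient mean.

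The cost is one model on data already collected, with lower precision. Across correlations of 0.1 to 0.7, power for a within-patient HR of 1.18 falls from 65% to 27% (4 segments) or from 73% to 32% (9 segments) at 300 events, against 82% for the pooled test. At 510 events it falls from 87% to 43% or from 92% to 49%. With 4 segments and 300 events, the 95% CI is about the estimate multiplied and divided by 1.15 to 1.27, against 1.12 for the pooled HR. Section 6.2 should state this as a range over assumed correlations. The result should be a reported estimate and not a significance gate.

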6.2 SAMPLE SIZE CONSIDERATIONS

A total of 9,000 patients will be enrolled with multi-vessel scans. It is expected based on the PROSPECT Study that at least 720 patients (8%) will experience a NC-MACE event. We expect to find approximately 3,000 patients with large LRP (max 4mm LCBI \geq 250). All 3,000 of these patients will be followed with phone calls for 2 years to identify those who have an event. We expect to observe at least 300 events in this group. From the 6,000 with no or small LRP, a random sample of 3,000 patients will also be followed to determine their event rate, and to examine with IVUS and angiograms those in whom events occur. Of the approximately 2,700 patients with large LRP who do not have an event, a 300 person sample will be selected for IVUS and angiographic analysis to investigate characteristics of the yellow spots that did not lead to events.

Vulnerable Patient Analysis

For hypothesis 1, we will test the hypothesis that there will be no association between the baseline value of max 4mm LCBI (over the entire area scanned) and the incidence of NC-MACE.

In PROSPECT registry results, the 24-month cumulative incidence of NC-MACE in patients was approximately 10%. Subsequent STEMI literature indicates that patients with large LRP will have a higher rate than that observed in PROSPECT.

For the power calculations below, we assumed 6,000 evaluable patients, an event rate between 4 and 8% in the overall LRP study, and a two-sided alpha of 0.05 with a standard deviation of 100 for max 4mm LCBI. Table 2

provides values for the power of the study to detect the following effect sizes: hazard ratio of 1.18, 1.20, and 1.22 per 100 unit increase in max 4mm LCBI (calculated in PASS 12). These results demonstrate that the study will have 80% power to detect a minimal effect size of 1.18 per 100 unit increase in the max 4mm LCBI with 6,000 patients and an overall cumulative incidence of 5% at 24 months. As described in section 5.3, interim analyses will be performed at 6 month intervals.

Table 2: Hypothesis 1: Power Calculation for Vulnerable Patient Hypothesis

2 Year cumulative incidence overall, patient level	Relative Risk per 100 unit increase in max 4mm LCBI		
	1.18	1.20	1.22
8%	0.95	0.98	0.99
7%	0.92	0.96	0.98
6%	0.88	0.93	0.97
5%	0.82	0.88	0.93
4%	0.73	0.81	0.87

Vulnerable Plaque Analysis

For hypothesis 2, we will test the hypothesis that there will be no association between the baseline value of max 4mm LCBI of the proximal, mid, or distal segment of a coronary artery and the incidence of NC-MACE.

For the vulnerable plaque analysis, we assumed that a patient will have a minimum of 50 mm of scanned target artery within at least 2 native epicardial arteries, yielding a minimum of 4 segments. Assuming that 24,000 segments (from 6,000 patients) will be available for analysis, a two sided alpha of 0.05 and a standard deviation of 100 LCBI units for max 4mm LCBI, Table 3 provides values for the power of the study to detect the following effect sizes: hazard ratio of 1.18, 1.20, and 1.22 (calculated by PASS 12). The study will have 80% power to detect a minimum effect size of 1.18 per 100 unit increase in the max 4mm LCBI with the minimum expected number of segments (24,000) and an overall cumulative incidence of 1.25% within the segments at 24 months.

Table 3: Hypothesis 2: Power Calculation for Vulnerable Plaque Hypothesis

2 Year cumulative incidence overall, segment level	Relative Risk per 100 unit increase in max 4mm LCBI		
	1.18	1.20	1.24
1.75%	0.92	0.96	0.98
1.50%	0.88	0.93	0.97
1.25%	0.82	0.88	0.93
1.00%	0.73	0.81	0.87
0.75%	0.60	0.69	0.76

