6.3 INTERIM ANALYSIS PLAN

As is evident from the power calculations provided in Section 5.2, for both the patient and segment level analysis, the LRP Study will have excellent power to detect relatively small increases in risk due to the presence of LRP.

The PROSPECT Study, with 700 patients, detected a hazard ratio of 5 for the presence of plaque burden > 70%. If the hazard ratio for increased LCBI reaches or exceeds 5, the LRP Study will provide definitive evidence that max 4mm LCBI predicts NC-MACE well before 6,000 patients have completed two-year follow-up. To provide an

opportunity for an early decision if this should occur, the LRP Outcomes Study will employ an interim analysis plan as described below.

When criteria for demonstrating an association between max 4mm LCBI and risk of NC-MACE have been met, the LRP Study will transition to a treatment study. This treatment study will include a control arm in which more detailed questions regarding the prognostic value of LCBI in various subgroups can be addressed in great detail.

The transition to a treatment study will require submission of a new protocol to the IRBs of the participating centers.

The interim analysis plan for the LRP Outcomes Study will be based on the Pocock spending function for repeated significance testing. This spending function will provide a greater opportunity for early stopping if strong associations emerge than would the O'Brien-Fleming or Haybittle-Peto spending functions. Specifically, review of accumulated data by the Data and Safety Monitoring Committee (DSMB) will occur on December 1, 2014 and at 6 month intervals thereafter until December 1, 2016. The DSMB will review the accumulated data to determine whether, in the multivariate analyses described in Section 5.1, both the vulnerable patient and the vulnerable plaque null hypotheses are statistically significant at the level required by the adjustment for repeated testing provided by the Pocock procedure. If those conditions are met, the DSMB may recommend termination of the study. If the study continues to the planned completion of two-year follow-up of all patients enrolled in the follow-up study, the two null hypotheses will be tested at the same significance level as that employed in the interim analyses. Additional information regarding the interim analysis plan will be provided in the Statistical Analysis Plan (SAP).

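### The power tables and both 80% power claims assume one test at two-sided 0.05, but the plan tests at a Pocock level over six looks; at 300 events power for HR 1.18 is about 0.65 to 0.72, not 0.82

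*Combined protocol and SAP*

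**What the plan says.** Section 6.2 sets the patient-level calculation at "a two-sided alpha of 0.05 with a standard deviation of 100 for max 4mm LCBI", with 6,000 evaluable patients and incidences from 4% to 8%. From Table 2 it concludes: "These results demonstrate that the study will have 80% power to detect a minimal effect size of 1.18 per 100 unit increase", at 5% incidence. The segment-level calculation uses "a two sided alpha of 0.05 and a standard deviation of 100 LCBI units for max 4mm LCBI" and 24,000 segments. From Table 3 it concludes: "The study will have 80% power to detect a minimum effect size of 1.18 per 100 unit increase in the max 4mm LCBI", at 1.25% incidence. Section 6.2 mentions the six-monthly interim analyses, but makes no allowance for them. It also gives an expected patient-level rate: "It is expected based on the PROSPECT Study that at least 720 patients (8%) will experience a NC-MACE event".

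Section 6.3 adopts a Pocock approach. Review of the accumulating data "will occur on December 1, 2014 and at 6 month intervals thereafter until December 1, 2016", which makes five interim looks. Termination may be recommended if "both the vulnerable patient and the vulnerable plaque null hypotheses are statistically significant at the level required by the adjustment for repeated testing". If the study runs to completion, "the two null hypotheses will be tested at the same significance level as that employed in the interim analyses". Section 6.3 states neither the overall alpha nor the nominal level, and leaves further interim detail to the SAP.

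**The concern.** Under Section 6.3 neither hypothesis is tested at 0.05 at any look, including the last. A Pocock boundary spends much of the error rate early, so its final test is markedly stricter than 0.05. Power computed at 0.05 therefore belongs to a different design.

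These are the only power statements for the two primary hypotheses, and Section 6.3 relies on them when it says the study is well able to detect small increases in risk. If they are too high, a null result would be judged against the wrong standard: at the headline scenario the chance of missing a true HR of 1.18 would be about 28% to 35%, not 18%.

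**Working it through.** **Inputs.** Section 6.2: two-sided alpha 0.05; SD 100 units, so the HR per 100 units is the HR per SD; 6,000 patients or 24,000 segments; HR 1.18. Section 6.3: looks on 1 Dec 2014, 1 Jun 2015, 1 Dec 2015, 1 Jun 2016 and 1 Dec 2016, plus the final test, so six looks at one common level. Section 5: enrolment January 2014 to December 2015, last follow-up December 2017. Assumption: overall two-sided alpha is 0.05 per hypothesis, carried over from Section 6.2.

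**Step 1: reproduce the plan.** For Cox regression on a continuous covariate with SD 1 (in units of 100),

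power = Φ(√D × ln HR − 1.96), with D = N × incidence.

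At 5%, D = 6,000 × 0.05 = 300 and √300 × ln 1.18 = 2.867, so power = Φ(0.907) = 0.818; Table 2 prints 0.82. For HR 1.18 at 8%, 7%, 6%, 5% and 4% the formula gives 0.952, 0.924, 0.881, 0.818 and 0.727, against 0.95, 0.92, 0.88, 0.82 and 0.73. The other Table 2 entries also match. Table 3 matches on the same basis (24,000 × 1.25% = 300), with its third column reproducing at the HR of 1.22 given in the text, not the 1.24 in the column header. Both tables are single-look calculations.

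**Step 2: the Pocock level.** Recursive numerical integration for an overall two-sided 0.05 gives:

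- six equally spaced looks: z = 2.453, nominal p = 0.0142;
- calendar spacing, looks at months 11, 17, 23, 29, 35 and 48, assuming uniform 24-month accrual and constant hazard: information fractions 0.107, 0.254, 0.463, 0.690, 0.856 and 1; z = 2.476, nominal p = 0.0133.

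**Step 3: power at that level, HR 1.18.** The final-test-only value is Φ(√D × ln 1.18 − z). At D = 300 this is Φ(2.867 − 2.453) = 0.660, or Φ(2.867 − 2.476) = 0.652. It is a lower bound, because an early stop also counts as success. Crossing at any look, by the same integration, is an upper bound for each hypothesis, because stopping requires both to cross. Ranges below run from calendar to equal spacing.

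| Events | Patient-level incidence | Segment-level incidence | Stated | Final test only | Any look |
|---|---|---|---|---|---|
| 480 | 8% | not tabulated | 0.95 | 0.875–0.880 | 0.903–0.906 |
| 420 | 7% | 1.75% | 0.92 | 0.820–0.826 | 0.858–0.863 |
| 360 | 6% | 1.50% | 0.88 | 0.747–0.754 | 0.796–0.803 |
| 300 | 5% | 1.25% | 0.82 | 0.652–0.660 | 0.715–0.722 |
| 240 | 4% | 1.00% | 0.73 | 0.535–0.544 | 0.610–0.619 |
| 180 | not tabulated | 0.75% | 0.60 | 0.399–0.408 | 0.483–0.491 |

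Simulating the rule that both must cross (1,000,000 trials, 300 events and HR 1.18 for each hypothesis, assumed correlations 0 to 0.9) gives per-hypothesis power of 0.68 to 0.70, between the two bounds.

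**Step 4: what 80% power requires.** Final test only: D = ((z + 0.842) / ln 1.18)² = 396 (equal) to 402 (calendar) events, that is 6.6% to 6.7% of patients or 1.65% to 1.67% of segments. Any look: 358 to 363 events, 6.0% to 6.1% or 1.49% to 1.51%. The single-look requirement is 287. With 300 events the HR detectable at 80% power is exp((z + 0.842) / √300) = 1.210 to 1.211 at the final test, or 1.198 to 1.200 at any look.

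**The case against.** The strongest reply is that the 5% row is a pessimistic scenario. Section 6.2 expects at least 8%, and the followed cohort is enriched: if 300 of the 720 expected events arise in the large-plaque group, and half of the other 420 fall among followed patients, there are 300 + 210 = 510 events. Power for HR 1.18 is then 0.90 (final test) to 0.92 (any look). This stands: on the plan's own expected rate the patient-level hypothesis remains well powered. It does not rescue the claim as written, which is made at 5%.

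For segments no expected rate is stated. If every one of 480 to 510 patient events were traced to one segment, the rate would be 2.0% to 2.1% (480/24,000 to 510/24,000). That is a ceiling, since Section 5.1.4 asks for the culprit site only where it can be identified. The 1.25% claim remains the only headline for that hypothesis.

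It is also fair that the overall alpha is unstated, that more interim detail is deferred to the SAP, and that Section 6.3 speaks of a spending function. But the method, the dates and the common final level are already fixed. Other readings give similar answers: five looks, if the last date is excluded, give 0.675 (final) and 0.730 (any look); a Pocock-type alpha-spending form gives 0.67 to 0.68 and 0.73. All are below 0.80.

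Finally, the detectable HR moves only from about 1.18 to 1.20 or 1.21, within the tabulated range, and the HR of 5 that motivates early stopping is unaffected. That limits the practical harm, but the stated power is still wrong for this design.

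**Conclusion.** The concern holds. Every entry in Tables 2 and 3 is a single-look figure, and both 80% claims overstate what the design delivers. At 300 events and HR 1.18, per-hypothesis power is between about 0.65 and 0.72, against a tabulated 0.82; allowing for the alternative readings of Section 6.3, it does not exceed 0.73. The shortfall is largest in the low-incidence rows and modest at 8%.

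The result rests on an overall two-sided 0.05 per hypothesis and six looks; the calendar figures also assume uniform accrual and constant hazard. Clustering of segments within patients and covariate adjustment in the definitive test are not included, and would change power further.

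**What to change.** Recompute Tables 2 and 3 at the six-look Pocock level. State the overall alpha, the nominal level and the number of looks. Show final-test-only and any-look values side by side, labelled as lower and upper bounds. Restate both headline claims: either 80% power at the final test for an HR of about 1.21 per 100 units at 5% patient-level (1.25% segment-level) incidence, or power between about 0.65 and 0.72 for HR 1.18. Keep the 8% row in view as the expected case for the patient-level hypothesis, at about 0.88 to 0.91. Adjust the statement in Section 6.3 that relies on the tables, and carry the same figures into the SAP.

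The cost is two recalculated tables and revised wording, with a less favourable stated power. Enrolment, boundary and look schedule do not change.
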